### 5.5.2 In Vivo Studies

The efficacy of MS1819-FD has been investigated in minipigs; in which experimental pancreatitis and EPI were induced by pancreatic duct ligation. Daily doses of MS1819-FD 10.5 mg or greater were administered once a day nearly completely corrected the CFA of approximately 20 kg minipigs (Aloulou 2015).

The safety of MS1819-FD has been investigated in 2 nonclinical regulatory trials whereby MS1819-FD was well tolerated at dosages up to 1000 mg/kg in rats and 250 mg/kg in minipigs for up to 13 weeks.

In summary, MS1819-FD was effective in minipigs and was nontoxic in both rodents and nonrodent species up to a maximum feasible dose of over 3 month's administration.

## 5.6 Clinical Studies with MS1819

### 5.6.1 FLIP110 First-in-Man Study with MS1819-FD

The efficacy and safety of MS1819-FD have been investigated in a first-in-man study, FLIP110. This exploratory clinical trial without predefined statistical analysis objectives, was a randomized, double blind, placebo controlled, parallel study.

Patients affected with chronic pancreatitis or pancreatectomy and severe EPI, were randomly assigned to 2 phases with an allocation ratio of 2:1 to receive MS1819-FD 20 mg 3 times a day or a 'dummy' placebo treatment identical in aspect and taste. Each treatment was given for a phase of 1 week after a 1-week washout phase.

Twelve patients were randomly included: 8 in MS1819-FD phase and 4 in the placebo phase. Three patients in the MS1819-FD phase were excluded from the per protocol (PP) analysis because of severe protocol deviations (ie, steatorrhea < 7 g/day in the baseline phase demonstrating the lack of significant EPI in these patients).

The primary endpoint of the study was defined as the relative change in steatorrhea compared with baseline. A nonstatistically significant difference of the primary endpoint was found between the 2 phases both in intent-to-treat (ITT:  $-14.6\% \pm 26.6$  in the MS1819-FD phase vs  $+16.9\% \pm 40$  in the placebo phase; not significant) and PP analysis ( $-15.8\% \pm 20.6$  in the MS1819-FD phase vs  $+16.9\% \pm 40$  in the placebo phase; not significant), respectively.

Secondary efficacy endpoints also support the efficacy of MS1819-FD compared with placebo in both ITT and PP populations, including the absolute change in CFA (ITT:  $+6.1 \pm 13.4$  vs  $-6.7\% \pm 11.0$ ), number of daily evacuations over 7 days (ITT:  $-19.2\% \pm 22.8$  vs  $+4.1\% \pm 11.7$ ;  $p = .09$ ), the weight of stools (ITT:  $-10.6\% \pm 27.4$  vs  $+25.5\% \pm 48.2$ ; not significant), and Bristol scale, which is a classification of the form of human feces to evaluate the effectiveness of treatments for diseases of the bowel (ITT:  $-5.13\% \pm 15.5$  vs  $+2.46\% \pm 16.6$ ;  $p < .0001$ ).

MS1819-FD was well tolerated with no serious adverse events (SAEs). Only 2 AEs were observed: constipation (2 patients in the MS1819 group) and hypoglycemia (2 patients in the MS1819 group and 1 patient in the placebo group).

In summary, the FLIP110 study supports the continued clinical investigations of the efficacy of higher doses of MS1819-FD using established surrogate biomarkers for EPI correction.

### 5.6.2 MS1819/16/01 Phase 2a Study with MS1819-SD

An open-label, dose escalation Phase 2a study (MS1819/16/01) was conducted to investigate the safety of escalating doses of MS1819-SD in 11 patients with EPI caused by chronic pancreatitis or pancreatectomy

The primary objective of this study was to investigate the safety of escalating doses of MS1819-SD (280 mg/day, 560 mg/day, 1120 mg/day, and 2240 mg/day). Safety assessments included immunoallergic side effects, digestive symptoms, and clinical laboratory tests. The secondary objective of this study was to investigate the efficacy of MS1819-SD by assessment of CFA.

Data from the first 8 treated patients are available and demonstrates clinical activity, where the greatest MS1819-SD response showed 14.5% improvement in CFA. The maximal absolute CFA response to treatment was 64.2%, with a trend to an inverse relationship to baseline CFA. Positive trends were observed on endpoints such as fecal nitrogen, Bristol stool scale, number of daily evacuations, and weight of stool, consistent with the CFA results.

No SAEs or notable mild to moderate events have been reported to date (Interim Analysis).

### 5.7 Rationale

Because of the limitations of porcine PERT therapy (outlined in [Section 5.3](#)), new drugs are required for the treatment of EPI due to CF or chronic pancreatitis. MS1819-SD has none of the highlighted drawbacks and the results from the FLIP110 study and preliminary results from the MS1819/16/01 study support the safety and efficacy of MS1819. Therefore, it is considered as an appropriate drug candidate for the treatment of EPI caused by CF.

This study, OPTION, is designed to assess the efficacy and safety of 2240 mg/day of MS1819-SD in patients with CF. This dose, recently studied in patients with chronic pancreatitis, is the highest dose studied to date, and was well tolerated. If this dose is well tolerated in patients with CF and shows evidence of improved digestion, higher doses may be considered for study.

### 5.8 Dose Justification

While this is the first study of MS1819-SD in patients with CF, previous studies in patients with chronic pancreatitis have included doses of MS1819-SD up to 2240 mg/day (see Section 5.6.2). A total of 11 patients have now received up to 3 weeks daily treatment; the tolerability has been acceptable. To bridge from these studies into patients with CF, we have set the dosage for this study at 2240 mg/day.

The use of mass (mg) for dose expression, rather than USP lipase units is the result of the biochemical difference between porcine pancreatic-derived lipase and the microbial-derived lipase from the yeast *Yarrowia lipolytica* (Aloulou et al, 2015). Porcine lipase is active at pH >7, while peak yeast-derived lipase activity occurs at pH 6. The USP assay for porcine lipase units is conducted using an olive oil substrate at pH 9, while the enzymatic activity for MS1819-SD is assayed using tributyrin as substrate at pH 6. No validated conversion factor is available for conversion of USP lipase units to tributyrin units. It has been suggested by the FDA for microbial-derived lipase products that mass rather than units be used for dose expression (Heubi et al, 2016).

## 6. STUDY OBJECTIVES

### 6.1 Primary Objectives

The primary objectives of this study are to assess the safety and efficacy of MS1819-SD vs porcine PERT in patients with EPI due to CF.

The primary safety objective of the study is to assess the safety and tolerability of a dose of 2240 mg/day of MS1819-SD in patients with EPI caused by CF. Efficacy will be evaluated by comparing treatment with MS1819-SD to treatment with porcine PERT.

## 7. INVESTIGATIONAL PLAN

### 7.1 Overall Study Design and Plan: Description

The OPTION study is a Phase 2, open-label, multicenter, 2x2 crossover trial to assess the safety and efficacy of MS1819-SD in patients with EPI due to CF in male and female patients aged 18 years or older. Efficacy will be evaluated by comparing treatment with MS1819-SD to treatment with porcine PERT. Refer to [Figure 1](#) for a flow chart of the study design.

During the treatment period, patients will be randomized to either MS1819-SD (2240 mg/day) or to their prestudy porcine PERT.

A Data and Safety Monitoring Board (DSMB), consisting of members external to AzurRx BioPharma, Inc., and including members of the Cystic Fibrosis Foundation Therapeutics, Inc. (CFFT) DSMB, will monitor safety throughout the trial. After the study is complete, the DSMB will review the efficacy/safety data.

Dosages will typically be fractionated as follows: 1/4 of the daily dose at each 3 main meals, and 1/8 at each of the 2 snacks (ie, 2240 mg/day will be fractionated as follows: 4 capsules of 140 mg with the morning, noontime, and evening meals, plus 2 capsules of 140 mg with the morning and evening snacks). Individual variations may occur as long as total daily dose is achieved.

The dose of prestudy porcine PERT will be the same dose that was being administered during the prestudy period.

The study will not employ a washout period between the first treatment period and the second treatment period. Recent experience with crossover lipase enzyme treatment from commercial PERTs to investigational lipase has demonstrated that symptoms of malabsorption may become evident within a matter of days, indicating little residual carryover effect of the original lipase (clintrials.gov NCT 02279498; clintrials.gov NCT0305140). Furthermore, the 3-week duration of treatment with either study agent is well established as sufficient to show the degree of lipase effectiveness (FDA Package Insert, CREON; FDA Package insert, PANCREAZE).

[figure not shown]
This study is divided into 4 main periods.

- Screening Period (up to 21 days)
- First Treatment Period (approximately 3 weeks) of the crossover design
- Second Treatment Period (approximately 3 weeks) of the crossover design
- End-of-Study/Early Withdrawal (approximately 2 weeks)

Refer to [Section 7.1.1 \(Table 1\)](#) for the Schedule of Assessments.

Figure 1: OPTION Study Design Flow Chart

**A Phase 2, Open-Label, Multicenter, 2x2 Crossover Trial to assess the Safety and Efficacy of MS1819-SD in Patients with Exocrine Pancreatic Insufficiency due to Cystic Fibrosis**

### 7.1.1 Schedule of Assessments

**Table 1: Schedule of Assessments**

	SCREENING		INITIAL TREATMENT PERIOD			SECOND TREATMENT PERIOD			END OF STUDY/EARLY TERMINATION	
	1 a	2 (T) b	3	4 (T) c	5 (T) c	6 d	7 (T) c	8 (T) c		
Visit Number	1 a	2 (T) b	3	4 (T) c	5 (T) c	6 d	7 (T) c	8 (T) c	9 d	10
Study Week	-3		1	1	2	3	4	5	6	8
Study Days	-21		1	8	15	17	29	36	38	56
Visit Window (days)	V1 to V2 interval $\leq$ 21 days			$\pm$ 2	$\pm$ 1	$\pm$ 7	$\pm$ 2	$\pm$ 2	$\pm$ 7	$\pm$ 2
Confirm scheduled date for next supervised confinement visit				X	X		X	X		
Study Treatment										
Randomization			X							
Instruct regarding prestudy PERT/Dispense study drug MS1819-SD			X			X			X	
Verify study drug count at the end of confinement						X			X	
Return MS1819-SD (only for those on MS1819-SD) at the end of confinement						X			X	
Record fat and protein intake and study drug taken at all meals and snacks						X			X	

	SCREENING		INITIAL TREATMENT PERIOD			SECOND TREATMENT PERIOD			END OF STUDY/EARLY TERMINATION	
	1 a	2 (T) b	3	4 (T) c	5 (T) c	6 d	7 (T) c	8 (T) c		
Visit Number	1 a	2 (T) b	3	4 (T) c	5 (T) c	6 d	7 (T) c	8 (T) c	9 d	10
Study Week	-3		1	1	2	3	4	5	6	8
Study Days	-21		1	8	15	17	29	36	38	56
Visit Window (days)	V1 to V2 interval $\leq$ 21 days			$\pm$ 2	$\pm$ 1	$\pm$ 7	$\pm$ 2	$\pm$ 2	$\pm$ 7	$\pm$ 2
Cross over to alternative treatment f						X				
Efficacy Measures										
Malabsorption signs & symptoms			X	X	X	X	X	X	X	
72-hour controlled diet record						X			X	
Marker-to-marker stool collection and stool weight g						X			X	
Laboratory Tests										
Urinalysis	X		X			X			X	
Pregnancy test (serum for V1 screening and urine dipstick for other visits) h	X		X			X		X	X	
Hematology, clinical chemistry, PT/INR, and aPTT i	X					X			X	
Fasting lipids (patient to come in)	X					X			X	

	SCREENING		INITIAL TREATMENT PERIOD			SECOND TREATMENT PERIOD			END OF STUDY/EARLY TERMINATION	
	1 a	2 (T) b	3	4 (T) c	5 (T) c	6 d	7 (T) c	8 (T) c		
Visit Number	1 a	2 (T) b	3	4 (T) c	5 (T) c	6 d	7 (T) c	8 (T) c	9 d	10
Study Week	-3		1	1	2	3	4	5	6	8
Study Days	-21		1	8	15	17	29	36	38	56
Visit Window (days)	V1 to V2 interval $\leq$ 21 days			$\pm$ 2	$\pm$ 1	$\pm$ 7	$\pm$ 2	$\pm$ 2	$\pm$ 7	$\pm$ 2
fasting status) and pre-albumin										
Vitamin A, D, E, and K	X		X			X			X	X
Serum samples for anti-LIP2 lipase antibodies and MS1819-SD concentrations			X			X			X	X
Fecal pancreatic elastase j	X									
Diagnostic Test										
Spirometry	X									
Resume Prescribed PERT										
Switch back to prescribed porcine PERT k									X	

A Screening procedures can occur up to 21 days before V1 through the first day of dosing (V3).

B This first study telephone call will occur once eligibility for the patient is determined. Instructions on the randomization visit will also be communicated and patients will be told to bring in their prestudy porcine with them for V3.

C Visits 4, 5, 7, and 8 are telephone visits to assess any changes to AEs and concomitant medications in addition to confirming the visit date for the next scheduled supervised confinement.

D Visit 6 and Visit 9 are the first and second scheduled confinement visits and can take up to 7 days. A 7 day window is permitted around the scheduled confinement for both V6 and V9 to accommodate for scheduling. Patient should bring their prestudy porcine PERT to V3.

---

- E The Focused Physical Exam will evaluate gastrointestinal tract, heart, and lungs.
- F At the end of V6 (after the last stool sample has been collected), Patients that were randomized to MS1819-SD will begin treatment with their prestudy porcine PERT. Patients that were randomized to their prestudy porcine PERT will begin treatment with MS1819-SD.
- G The stool samples and weight will be sent and analysed at the central laboratory.
- H A serum pregnancy test must be conducted in females of reproductive potential at screening. Pregnancy status will be re-evaluated via urine pregnancy test in these Patients at Visit 3,6,9 and at the End-of-Study or Early Termination visit.
- I On the basis of laboratory safety values, unscheduled hepatic monitoring testing may be performed in Patients with new, clinically-meaningful increases in liver function tests occurring during the study, in consultation with study designated Medical Monitor. These tests are to be done through the central labs.
- J Fecal pancreatic elastase will be sent and analysed by the central laboratory.
- K At the end of V9, Patients should resume their prescribed porcine PERT. For Patients that were on their prescribed porcine PERT during V9 no change will be needed.

## 7.2 Study Endpoints

### 7.2.1 Primary Efficacy Endpoints

Safety and efficacy will be primary endpoints. Safety will be evaluated by descriptive methods. Efficacy will be assessed by noninferiority of CFA, between the MS1819-SD treatment vs the porcine PERT treatment.

### 7.2.2 Secondary Efficacy Endpoints

The secondary efficacy endpoints of the study include:

- A comparison of 72-hour stool weights, MS1819-SD vs porcine PERT
- Signs and symptoms of malabsorption
  - Stool frequency (number of bowel movements per day)
  - Stool consistency (graded as 0=hard, 1=formed/normal, 2=soft, 3=watery, or 4=overt diarrhea)
  - Bloating (graded as 0=none, 1=mild, 2=moderate, 3=severe)
  - Abdominal pain (graded as 0=none, 1=mild, 2=moderate, or 3=severe)
  - Flatulence (graded as 0=none, 1=mild, 2=moderate, or 3=severe)
  - Incidence of visible oil/grease in stool (Yes/No)
  - Increased stool quantity (graded as 0=none, 1=mild, 2=moderate, or 3=severe)
  - Worsening of overall bowel habit (graded as 0=none, 1=mild, 2=moderate, or 3=severe)
- CNA
- Body weight
- Body mass index
- Serum liposoluble vitamins A, D, E and K

### 7.2.3 Safety Endpoints

AEs, SAEs and drop outs.

In addition, laboratory test results will be summarized ([Section 15.2](#)):

- Hematology
- Biochemistry
- Fasting lipid profile
- Urinalysis
- Serum MS1819 concentrations
- Antibodies against LIP2 lipase

### 7.3 Discussion of Study Design

#### 7.3.1 Number of Planned Patients

Approximately 30 patients are planned to complete the study pending a safety assessment after each group completes their clinical treatments and evaluations. To account for a possible 20% dropout rate, approximately 38 patients are planned to be enrolled.

The statistical considerations on which the planned number of patients is based are described in [Section 10](#).

#### 7.3.2 Inclusion Criteria

To be eligible for study entry, patients must satisfy all of the following inclusion criteria:

1. Signed and dated informed consent form by patient as required by AzurRx or designee and appropriate Institutional Review Board/Independent Ethics Committee (IRB/IEC)
2. Age  $\geq 18$  years at the time of screening
3. Male or female
4. Cystic fibrosis, based on 2 clinical features consistent with CF, plus initial diagnostic sweat chloride  $\geq 60$  mmol/L by quantitative pilocarpine iontophoresis or genotype
5. Under stable dose of porcine PERT  $\geq 1$  month; stable dose is defined as dose of medication not changed during this time period, and the medication must be commercially available and be administered in the recommended dose range.
6. A fair or better nutritional status as defined by:
  - BMI  $\geq 16.0$  kg/m^2 for female patients  $\geq 18$  years of age, or
  - BMI  $\geq 16.5$  kg/m^2 for male patients  $\geq 18$  years of age

7. Fecal elastase <100 µg/g of stool at screening
8. Clinically stable with no documented evidence of significant respiratory symptoms that would require administration of intravenous antibiotics, oxygen supplementation, or hospitalization within 30 days of screening or during the screening period.
9. Male and Female patients, if of childbearing potential, must use a reliable method of contraception during the study. A reliable method of birth control is defined as one of the following: oral or injectable contraceptives, intrauterine device, contraceptive implants, tubal ligation, hysterectomy, or a double-barrier method (diaphragm with spermicidal foam or jelly, or a condom), abstinence or vasectomy. Periodic abstinence (calendar, symptothermal, or post-ovulation methods) is not an acceptable method of contraception. The preferred and usual lifestyle of the patient must also be evaluated in determining if sexual abstinence is a reliable method of birth control
10. Be considered reliable and capable of adhering to the protocol, according to the judgment of the Investigator

### 7.3.3 Exclusion Criteria

Patients will be excluded from the study if one or more of the following criteria are applicable:

1. Established or suspected fibrosing colonopathy
2. Total or partial gastrectomy
3. A history of solid organ transplant, or significant surgical resection of the bowel; significant resection of the bowel is defined as any resection of the terminal ileum or ileocecal valve. Patients who have had qualitative, long-term changes in nutritional status after any other bowel resection (eg, increased or new need for pancreatic enzyme supplementation compared with preoperative status to maintain the same nutritional status) should also be excluded.
4. Any chronic diarrheal illness unrelated to pancreatic insufficiency (eg, infectious gastroenteritis, sprue, inflammatory bowel disease)
5. Known hypersensitivity or other severe reaction to any ingredient of the investigational medicinal product (IMP)
6. Alanine aminotransferase (ALT) or aspartate aminotransferase (AST) level  $\geq 5 \times$ upper limit of normal (ULN) or total bilirubin level  $\geq 1.5 \times$ ULN at the Screening visit, unless due to Gilbert's syndrome. Cases of suspected or confirmed Gilbert's syndrome should be discussed with the Medical Monitor.

7. Signs and/or symptoms of liver cirrhosis or portal hypertension (eg, splenomegaly, ascites, esophageal varices), or documented liver disease unrelated to CF
8. Patients with a known allergy to the stool marker (FD&C Blue #2)
9. Feeding via an enteral tube during 6 months before screening
10. Routine use of anti-diarrheals, anti-spasmatics, or cathartic laxatives, or a change in chronic osmotic laxatives (eg, polyethylene glycol) regimen in the previous 3 months
11. History of severe constipation with <1 evacuation/week under appropriate laxative therapy within the last 12 months before screening
12. Documentation of distal intestinal pseudo-obstruction syndrome within the last 12 months before screening
13. Forced expiratory volume  $\leq 30\%$  at the Screening visit
14. Lactation or known pregnancy or positive pregnancy test at screening for women of childbearing potential
15. Participation in another clinical study involving an IMP within 30 days before inclusion or concomitantly with this study
16. Patient's with poorly controlled diabetes according to the Investigator's judgment

#### 7.3.4 Removal of Patients from the Study

A patient may be withdrawn from the study at any time for any of the following reasons:

- Loss to follow-up
- Withdrawal of consent, for any reason, at any time
- Major protocol deviations that could compromise the interpretation of the results
- Occurrence of an immunoallergic reaction
- Occurrence of an adverse reaction (ie, an SAE related to IMP) that justifies the discontinuation of the IMP
- Pregnancy

The date of withdrawal and the reason for withdrawal must be fully documented in the case report form (CRF) and a short narrative description should be added in the patient's medical records.

If at the time of withdrawal, the patient has received the investigational study product (partially or totally), study staff should encourage the patient to attend the Early Withdrawal

---

Visit for follow-up safety investigations. These patients will be included in the ITT efficacy analysis and safety analysis.

If the reason for discontinuation is an AE, then the Investigator will seek to obtain follow-up information and to document the event until its resolution or stabilization. In any case, the Investigator will take all necessary measures to ensure the patient's safety and ensure the patient is treated in accordance with local standard of care.

If a patient is lost to follow-up, then the Investigator should make every effort to obtain maximum information on the reasons for the nonattendance to the visit and on the patient's state of health. All attempts will be documented in the patient's medical records.

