### 10.3 Analysis Sets

- Randomized set: patients as randomized. Unless specified otherwise, this set will be used for all patient listings and summaries of patient disposition.
- Safety Set: patients receiving at least one dose of treatment. Patients will be analyzed according to the treatment actually received. The Safety Set will be

---

used for all analyses of safety endpoints unless specified otherwise and for the presentation of patients in listings related to dosing of study drug.

- Efficacy sets:
  - ITT Set: Patients as randomized and receiving at least one dose of treatment. The ITT set is considered as the primary set for the efficacy analysis. The ITT set will be used for all analyses of efficacy endpoints.
  - Per Protocol Set: Subset of the ITT set comprising all patients who do not violate the terms of the protocol in a way that would affect the study outcome significantly, as determined by the study clinician. Protocol deviations will be captured throughout the study and classified as minor or major and reviewed at a data review meeting before database lock. Attendees will include appropriate individuals from the Sponsor and contract research organization. Each major deviation will be categorized as either important or not important with respect to the effect on the primary endpoint analysis. A sensitivity analysis will be performed in the Per Protocol Set.

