1. PURPOSE OF THE ANALYSES

The statistical analysis plan (SAP) is being developed after review of the AzurRx Biopharma, Inc. (AzurRx), protocol number AZ-CF2001, but before any analyses of the data. The SAP contains detailed information to aid in the implementation of the statistical analyses and reporting of the study data for use in the clinical study report (CSR). This SAP is being written with due consideration of the recommendations outlined in the most recent International Conference on Harmonisation (ICH) E9 Guideline entitled Guidance for Industry: Statistical Principles for Clinical Trials and the most recent ICH E3 Guideline, entitled Guidance for Industry: Structure and Content of Clinical Study Reports.

This SAP describes the analysis sets that will be analyzed, the subject characteristics parameters, the efficacy parameters, and the safety parameters that will be evaluated. The details of the specific statistical methods that will be used will be provided in this SAP. If differences occur between analyses described in the SAP and the current protocol, those found in this SAP will assume primacy. If additional analyses are required to supplement the planned analyses described in this SAP, they may be completed and will be identified in the CSR. Table and listing specifications are provided in a separate document.

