4.1 Modified Intent-to-Treat Population

The modified intent-to-treat (mITT) population includes all randomized subjects who receive at least 1 dose of treatment and have at least 1 sufficient stool sample. A stool sample will be considered sufficient if the date and time associated with the second blue dye marker is recorded, indicating that the stool sample collection is complete. The mITT will be used for efficacy analyses. Subjects will be analyzed according to the treatment group to which they were randomized regardless of the actual treatment received, unless stated otherwise.

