9. EFFICACY EVALUATION

9.1 Overview of Efficacy Analysis Issues

9.1.1 Handling of Dropouts or Missing Data

Missing data will not be replaced.

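### Withdrawing patients from the study for major protocol deviations stops later CFA collection and lets a discretionary, open-label decision shape the primary data

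*Protocol*

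**What the plan says.** Protocol 7.3.4 opens with "A patient may be withdrawn from the study at any time for any of the following reasons", and one of the reasons is "Major protocol deviations that could compromise the interpretation of the results". The rule is permissive and concerns the study, not only the treatment. It names no decision-maker and gives no definition of a major deviation for use while the patient is on study. For patients who have had study product by then, the section adds: "These patients will be included in the ITT efficacy analysis and safety analysis".

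Protocol 10.3 defines the ITT set as "Patients as randomized and receiving at least one dose of treatment" and makes it the primary efficacy set. SAP 4.1 replaces it with an mITT set that "includes all randomized subjects who receive at least 1 dose of treatment and have at least 1 sufficient stool sample". SAP 1 states that where the two documents differ, "those found in this SAP will assume primacy". SAP 11.1, which lists differences from the protocol, does not mention this one.

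On missing values, SAP 9.1.1 says "Missing data will not be replaced", and SAP 9.2.1 says the same of CFA in particular. Protocol 8.3.3 gives the Early Withdrawal visit the same procedures as Visit 10, and stool collection is not among them.

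Deviations have their own route. Protocol 10.3 and SAP 5.2 have them classified as major or minor at a data review meeting before database lock, and SAP 4.2 keeps major deviations that could affect efficacy out of the PP set.

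**The concern.** Whether a deviation spoils the interpretation of a result is normally settled at the analysis stage, under a written rule, with the data still collected. Here it can be settled during the study by ending the patient's participation. The trial is open-label, so whoever decides knows the current treatment and may know how the patient is doing on it. The major or minor label is confirmed only later, so a patient can be removed on a classification that nobody has yet confirmed.

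Two things are at stake. The first is who contributes to the primary noninferiority comparison, since the primary set can drift towards a per-protocol set without any analysis rule saying so. The second is avoidable loss of data in a trial planned around 30 completers.

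**Working it through.** **1. What happens to a withdrawn patient's CFA**

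| Withdrawn | CFA available | Protocol ITT (10.3) | SAP mITT (4.1) | Contribution to the primary model |
|---|---|---|---|---|
| Before the Visit 6 collection is complete | none | in | out | none |
| In period 2, before the Visit 9 collection is complete | Visit 6 only | in | in | one value, no within-patient contrast |
| After the Visit 9 collection | both | in | in | full |

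In the first row, the inclusion promised in 7.3.4 cannot be carried out: the patient has no CFA, nothing is imputed, and the SAP set leaves the patient out. In the second row the promise is kept, but with half the information.

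**2. The plan's own sample size**

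Inputs from Protocol 10.2: margin 15, SD of paired differences 20, true difference -4, one-sided alpha 0.025, 30 completers, 20% dropout. A noncentral t calculation with n - 2 degrees of freedom gives 82.8% power at n = 30, consistent with the stated figure of around 80%. Inflation: 30 / 0.80 = 37.5, so 38, as stated. At the difference the protocol actually expects, -8, power at n = 30 is 45.7%.

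**3. Cost in precision**

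The standard error of the treatment difference is 20/√30 = 3.65 with 30 complete pairs and 20/√38 = 3.24 with 38. With 30 pairs plus 8 patients who have period 1 only, the planned mixed model gives 3.49 to 3.59 for an assumed between-patient variance of 50 to 400. Patients with one period therefore help a little, but much less than complete pairs.

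As an upper bound, suppose all 8 allowed dropouts were deviation withdrawals and could be kept. Power would rise from 82.8% to 91.0% at -4, and from 45.7% to 55.6% at -8. The documents do not say how many dropouts would be of this kind.

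**4. Possible selection effect (assumed inputs)**

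Assume that k of 38 patients are lost with both values, that their true MS1819-minus-PERT difference is D, and that the rest have -8. Then:

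- full mean = (k × D + (38 - k) × (-8)) / 38
- analysed mean = -8
- shift = k × (-8 - D) / 38

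| k | D | Full mean | Shift towards noninferiority |
|---|---|---|---|
| 1 | -20 | (-20 - 296)/38 = -8.3 | 12/38 = 0.3 |
| 1 | -40 | (-40 - 296)/38 = -8.8 | 32/38 = 0.8 |
| 3 | -20 | (-60 - 280)/38 = -8.9 | 36/38 = 0.9 |
| 3 | -40 | (-120 - 280)/38 = -10.5 | 96/38 = 2.5 |

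The distance from -8 to the margin is 7 points.

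The chance of claiming noninferiority can be compared using each set's own size and SD, with no other dropout. The full-set SD is √(400 + p(1 - p)(D + 8)²), where p = k/38.

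- **k = 1, D = -20:** 51% with all 38 (SD 20.1) against 54% with 37 (SD 20).
- **k = 3, D = -40:** 23% with all 38 (SD 21.8) against 52% with 35 (SD 20).

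The result depends almost entirely on D and k, and neither is in the documents. If the lost patients were those doing badly on PERT, the sign of the shift would reverse.

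**The case against.** The rule says a patient may be withdrawn, not must. Nothing ties it to the MS1819 period or to poor response, and failure to respond is not a listed reason. A patient doing badly could equally leave by withdrawing consent, which no change to this bullet would prevent. The gap between the ITT statement and the mITT set also arises for every other withdrawal reason. All of this stands, and it limits the point to an avoidable route by which data can be lost.

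There is also a case for removal in a noninferiority trial: values from patients who deviated, for example by taking the other product, can pull the difference towards zero. That is a reason to report the PP analysis beside the primary one, as the plan does. It does not justify leaving the data uncollected.

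A reader might infer that the plan deletes CFA values because of a deviation. It does not. The only exclusion of a collected CFA in SAP 9.2.1 is for a treatment switch during confinement before stool collection ends.

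A reader might also infer that the rule favours MS1819. Some features make that plausible. Protocol 7.1 says symptoms may appear within days of moving to an investigational lipase, antidiarrhoeals are prohibited, and SAP 7 computes compliance for MS1819 only. None of this shows that such removals would happen, how often, or that they would outnumber removals on PERT.

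**Conclusion.** The point holds as a weakness of design and as an inconsistency between the documents. Protocol 7.3.4 lets an undefined, discretionary judgement about interpretability end CFA collection in an open-label noninferiority trial. Under the governing SAP, that judgement can decide whether a patient enters the primary set at all (withdrawn before the Visit 6 collection is complete) or contributes one value instead of a pair (withdrawn in period 2). For the first group, the ITT statement in 7.3.4 cannot be met.

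The documents do not determine the size or direction of any bias. The 0.3 to 2.5 points rest on assumed counts (1 to 3 of 38), assumed differences (-20 to -40 against -8) and the loss of both values, so they are a range for illustration and not an estimate. The recommendation does not depend on them, because the data loss is avoidable and deviations already have a place in the plan.

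**What to change.** In Protocol 7.3.4, remove interpretability of the results as a reason for withdrawal from the study. State instead that:

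- the deviation is recorded;
- the Visit 6 and Visit 9 collections continue where the patient's consent is in place and the investigator sees no safety reason against it;
- the deviation is addressed in the PP analysis after the pre-lock review.

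Leave the consent and safety reasons in 7.3.4, and the treatment-switch exclusion in SAP 9.2.1, unchanged. The change concerns data collection only and does not touch decisions about a patient's treatment.

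Reconcile the ITT statement in 7.3.4 and the ITT set in Protocol 10.3 with the mITT set in SAP 4.1, and list the difference in SAP 11.1. Report the number of withdrawals for each reason by treatment at the time of withdrawal. Because other reasons for withdrawal will still leave gaps, add one sensitivity analysis for missing CFA.

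The cost is an edited bullet, a few sentences and some additional confinement visits completed. Some CFA values from patients with deviations will enter the primary analysis, so the primary and PP results should be read together.
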